5.1 Efficacy Analysis

Due to the extremely low enrollment to the trial and its early termination status, the efficacy analyses specified in the SAP do not need to be conducted in the final analysis, except providing summary statistics.

5.1.1 Data Sets Analyzed

The following samples are defined for this trial:

- Treatment Phase A Safety Sample consists of all subjects who receive at least one dose of investigational medicinal product (IMP) in Treatment Phase A of the trial.
- Treatment Phase B Safety Sample for responders consists of all randomized Late Withdrawal subjects who receive at least one dose of IMP in Treatment Phase B of the trial and all randomized Early Withdrawal subjects.
- Treatment Phase B Safety Sample for nonresponders consists of all nonresponders who receive at least one dose of IMP or standard of care in Treatment Phase B of the trial.
- Treatment Phase A Efficacy Sample consists of all subjects who are in the Treatment Phase A Safety Sample and have baseline and at least one postbaseline serum sodium evaluation in Treatment Phase A.
- Treatment Phase B Efficacy Sample for the responders is based on the intent-to-treat (ITT) principle; the full analysis dataset will be composed of all subjects who are in the Treatment Phase B Safety Sample and have both baseline and at least one postrandomization serum sodium evaluation in Treatment Phase B.

- Treatment Phase B Efficacy Sample for the nonresponders consists of all subjects who are in the Treatment Phase B Safety Sample for nonresponders and have both baseline and at least one postbaseline serum sodium evaluation in Treatment Phase B.

The core dataset for efficacy analyses will be based on the ITT population. In order to handle missing data and restrictions imposed by different types of analyses (eg, change from baseline analysis), datasets derived from the ITT dataset will be used for the efficacy analyses.

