#### All Subjects

All subjects will have serum sodium levels measured at 8, 12, and 24 hours post-first dose and thereafter every 12 ( $\pm 4$ ) hours through completion of Treatment Phase B. In addition to serum sodium samples obtained for treatment qualification and efficacy endpoints, supplemental samples for the purposes of safety assessment will be obtained on Day 1 at 4 to 6 (-1 to + 0.25) hours postdose and at 18 ( $\pm 1$ ) hours postdose. This sodium safety assessment will be repeated at 6 (-1 to + 0.25) and 18 ( $\pm 1$ ) hours postdose each day for the remainder of titration.

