##### **For all subjects classified as Responders at the end of Treatment Phase A**

- 1) Randomize the subject to the Early or Late Withdrawal group using the trial's interactive web response system (IWRS).

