## 7.2 Datasets for Analysis

The following samples are defined for this trial:

- Enrolled Sample consists of all subjects for whom an ICF/assent form was signed for the trial.
- Treatment Phase A Safety Sample consists of all subjects who receive at least one dose of IMP in Treatment Phase A of the trial.
- Treatment Phase B Safety Sample consists of all randomized late withdrawal subjects who receive at least one dose of IMP in Treatment Phase B of the trial and all randomized early withdrawal subjects.
- Treatment Phase A Efficacy Sample consists of all subjects who are in Treatment Phase A Safety Sample and have baseline and at least one post-baseline efficacy evaluation in Treatment Phase A.
- Treatment Phase B Efficacy Sample is based on the intent-to-treat (ITT) principle; the full analysis dataset will be composed of all subjects who are in the Treatment Phase B Safety Sample and have both baseline and at least one post-baseline efficacy evaluation in Treatment Phase B.

Core dataset for efficacy analyses will be based on the ITT population. In order to handle missing data and restrictions imposed by different types of analyses (eg, change from baseline analysis), datasets derived from the ITT dataset will be used for the efficacy analyses.

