5.1.7 Primary Outcome Analysis

5.1.7.1 Analysis of the Primary Outcome Endpoint

The primary endpoint in this trial is the change in serum sodium level for responders from Day 2 (or 2a) at the end of Treatment Phase A (where all subjects receive tolvaptan) to the end of Treatment Phase B for the Early compared to Late Withdrawal groups. The null hypothesis of this comparison is that there is no difference between the Late and the Early Withdrawal groups in change of serum sodium level from Day 2 (or 2a) at the end of Treatment Phase A to the end of Treatment Phase B. The analysis of the primary endpoint is based on the Treatment Phase B Efficacy Sample. Once a subject is randomized to Treatment Phase B, any additional therapies for the purpose of raising serum sodium, including fluid restriction, will be considered rescue therapy. Upon receipt of rescue therapy, a subject's endpoint data will be collected and then censored from the efficacy analysis thereafter unless specified. The primary analysis of this protocol is based on the data collected in this manner.

A sensitivity analysis will be provided in which serum sodium data collected for an Early Withdrawal subject under fluid restriction will not be censored for the analysis of the primary endpoint. This sensitivity analysis would become the primary analysis if at least 30% of the Early Withdrawal subjects do not have serum sodium data at 24 and 48 hours postrandomization due to application of fluid restriction in the withdrawal phase of the protocol.

The MMRM analysis with an unstructured variance covariance structure based on the OC dataset will be performed on the primary endpoint. The MM [REDACTED] clude

fixed effect of treatment, age subgroup [REDACTED], serum sodium response subgroup [REDACTED], underlying etiology [REDACTED], visit, treatment visit interaction, and covariate of baseline and baseline visit interaction. A statistical test of the least squares (LS) mean differences between treatment groups at the end of Treatment Phase B of the MMRM analysis will serve as the primary analysis.

As a sensitivity analysis, analysis of covariance (ANCOVA) with baseline value as covariate and treatment, age subgroup, serum sodium response subgroup, and underlying etiology of hyponatremia as factors will be applied to the LOCF dataset. Treatment comparison between the Late and Early Withdrawal groups will be conducted by comparing their LS.

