5.1.7.2 Technical Computational Details for Primary Outcome Analysis

- 1) Baseline for Treatment Phase B is the last evaluation of serum sodium at the end of Treatment Phase A.
- 2) For the Early Withdrawal group, the serum sodium collected at 72 hours post-last dose on the CRF will be used to define the endpoint of Treatment Phase B. For the Late Withdrawal group, the serum sodium collected at 24 hours post-dose (Trough) of Day 4 on the CRF will be used to define the endpoint of Treatment Phase B.
- 3) The MMRM analysis for the primary endpoint will be analyzed using PROC MIXED of SAS (with default REML option). Specifically, the following SAS statements will be used for the primary analysis:

```
proc mixed;
class treatment visit subject agesubgrp responsesubgrp etiologysubgrp;
model change =agesubgrp responsesubgrp etiologysubgrp treatment visit
treatment*visit baseline baseline*visit/ s ddfm=kr;
repeated visit / type=un sub=subject;
lsmeans treatment*visit / pdiff cl alpha=0.05;
run;
```
- 4) In case there is a convergence problem in the MMRM model with the unstructured variance covariance matrix, the following variance covariance matrix structures will be used in the order of 1) heterogeneous toeplitz, 2) heterogeneous autoregressive of order 1, and 3) heterogeneous compound symmetry. The first (co)variance structure which does not have a convergence problem will be the one used for the analysis. If a structured covariance has to be used, the “sandwich” estimator of the variance covariance matrix of the fixed effects parameters will be used in order to deal with possible model misspecification of the covariance matrix.
- 5) Medications for rescue therapy (with indication of hyponatremia) include:
Rescue therapy is defined as any level of fluid restriction, hypertonic saline, isotonic saline (with or without diuretic for purpose of increasing the serum sodium level), plasmapheresis/dialysis, demeclocycline, urea, lithium, commercially available

vaptans, or any treatment intended to raise the level of serum sodium at any time during the trial.

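### The Phase B efficacy set is called ITT but drops undosed subjects from the Late Withdrawal arm only

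*SAP*

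**What the plan says.** SAP 5.1.1 describes the responders' Phase B Efficacy Sample as resting on the ITT principle, then gives its membership: "the full analysis dataset will be composed of all subjects who are in the Treatment Phase B Safety Sample" and who also have a baseline and at least one post-randomization sodium value. The Safety Sample it draws on admits randomized Late Withdrawal subjects "who receive at least one dose of IMP in Treatment Phase B of the trial and all randomized Early Withdrawal subjects". Protocol 7.2 has the same rule: Late Withdrawal subjects "who receive at least one dose of IMP in Treatment Phase B of the trial and all randomized early withdrawal subjects".

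SAP 5.1.7.1 bases the primary endpoint on this set. Its MMRM includes treatment, the three stratification factors, and "visit, treatment visit interaction, and covariate of baseline and baseline visit interaction". For Late Withdrawal, SAP 5.1.7.2 item 2 says "the serum sodium collected at 24 hours post-dose (Trough) of Day 4 on the CRF will be used to define the endpoint" of Phase B. It does not say what to use when there was no Day 4 dose.

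SAP 5.1 states that, given low enrollment and early termination, the efficacy analyses "do not need to be conducted in the final analysis, except providing summary statistics".

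**The concern.** The sodium-availability condition applies to both arms; the dose condition applies to one. An analysis by intent to treat keeps everyone in the arm to which they were randomized, whatever they then received. Here, receipt of treatment after randomization decides membership in Late Withdrawal and is irrelevant in Early Withdrawal.

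The exclusion need not be unrelated to outcome. Protocol 3.2.4.1 withholds the next dose when sodium has risen too fast or is too high, and the arms are open-label. The Late Withdrawal subjects who drop out of the set may therefore differ in expected sodium change from those who remain, while their counterparts in Early Withdrawal are still counted. What is at stake is the comparability of the arms in the by-arm results, and whether a report may call the set ITT.

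Rescued subjects and subjects who leave the trial are outside this point. Censoring and the sodium requirement treat them the same way under either definition.

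**Working it through.** **Can the excluded subject exist?**

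- Protocol 3.7.1.3.1 places randomization on Day 3 and lists it ahead of the Late Withdrawal Day 3 dose.
- Protocol 3.2.4.1 holds the next dose after a rise above 8 mEq/L in 24 hours or a level above 140 mEq/L; interruption and withdrawal are among the options to be considered.
- Protocol 3.10 provides for subjects who stop tolvaptan before the end of Phase B but remain for assessments.

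So a responder can be randomized to Late Withdrawal, receive no Phase B dose and still have post-randomization sodium values. Neither document restores that subject to the efficacy set. The ITT population named at the end of both sections is not separately defined.

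**The plan's own figure.** Inputs from SAP 4.1: 70 randomized 1:1, difference 4, SD 5, two-sided alpha 0.05. The standard error is 5 × √(2/35) = 1.195. Power at 35 per arm is 91.0% by the t-test and 91.7% by the normal approximation, so the stated 90% reproduces.

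**Loss of power.** With 2 or 4 of 35 Late Withdrawal subjects excluded, t-test power is 90.1% or 89.2%. Power is not the issue.

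**All-randomized difference against the planned set.** Assume k of 35 Late Withdrawal subjects are undosed and then behave like Early Withdrawal. The all-randomized difference is 4 × (1 − k/35):

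| k | Difference (mEq/L) | Gap from 4.0 | Gap / 1.195 |
|---|---|---|---|
| 2 | 3.77 | 0.23 | 0.19 |
| 3 | 3.66 | 0.34 | 0.29 |
| 4 | 3.54 | 0.46 | 0.38 |

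For a small final sample (size assumed), one undosed subject of 10 gives 4 × (1 − 1/10) = 3.6, and one of 5 gives 4 × (1 − 1/5) = 3.2.

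**With no drug effect.** Simulation: 4000 runs, 35 per arm, total SD of change 5, Phase B baseline mean 134 and SD 4, slope of change on baseline −0.4, top 2 or top 4 Late Withdrawal subjects removed. Every input except the SD of 5 and the 35 per arm is an assumption.

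| Selection on | Estimate from the planned set | 2 removed | 4 removed |
|---|---|---|---|
| Baseline sodium | Unadjusted | 0.16 | 0.34 |
| Baseline sodium | Baseline-adjusted | −0.02 | 0.00 |
| Trait outside the model (1.5 per SD) | Baseline-adjusted | 0.18 | 0.34 |

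The non-zero differences favour Late Withdrawal. The all-randomized set gives about 0 in each case. A repeat run gave 0.20 and 0.34 for the first row, and 0.14 and 0.31 for the third.

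**General form.** The bias is f × D, where f is the excluded share and D is the mean change of retained minus excluded subjects. For D of 2 to 6 mEq/L (assumed), 2/35 × D is 0.11 to 0.34 and 4/35 × D is 0.23 to 0.69. The documents do not fix the sign of D.

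**The case against.** The strongest reply is that nothing inferential depends on the set. SAP 5.1 removes the tests, so the 35-per-arm figures describe a trial that was not completed. No document shows that an undosed Late Withdrawal subject occurred, or says which set the summaries will use. This stands, and it limits the harm to the label and to possible skew in the by-arm summaries.

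Second, the routes are narrow. Protocol 3.12 calls deviation from assigned treatment noncompliance, and 3.8.3(c) requires withdrawal for noncompliance, so many who decline dosing would leave the trial. One Phase B dose keeps a subject in the set, so a sodium-driven exclusion requires both doses to be missed. Under the assumed baseline, P(sodium > 140) is P(Z > 1.5) = 6.7%, or about 2.3 of 35, on Day 3 alone; the range of 2 to 4 is therefore not conservative. These points narrow the routes. They do not close them, because Protocol 3.10 expects some subjects to stop drug and stay, and the hold for rapid rise adds to the hold on level.

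Third, the 3.77 to 3.54 range compares two target quantities, assignment against treatment received; it is not bias under the null. Baseline adjustment removes selection on measured baseline, and the response stratum (cut at 7 mEq/L in Protocol 3.3) captures part of the rate of rise. Both are correct. Symptoms, clinical judgement and the rest of the rise stay outside the model, and unadjusted summaries have no such protection.

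Fourth, compliance (SAP 5.1.5) and the deviation listing (SAP 5.1.6) would reveal some undosed subjects. That is partial, since a hold directed by the protocol may not count as a deviation.

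**Conclusion.** The concern holds. The dose condition makes the Phase B Efficacy Sample a modified ITT set in one arm, contrary to its label, in both the SAP and the protocol. Under the stated assumptions the effect is modest: a gap of 0.23 to 0.46 mEq/L, or 0.19 to 0.38 of the design standard error, for 2 to 4 undosed of 35, and proportionally more in a very small sample. The wording defect is certain. The numerical harm depends on an undosed rate that the documents do not give, and it is zero if no such subject occurred. With no test planned, this should be corrected before the summaries are produced, but it does not threaten a confirmatory conclusion.

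**What to change.** In SAP 5.1.1, and in Protocol 7.2 if it is amended again, define the Phase B Efficacy Sample as all randomized responders, analysed in their assigned arm, who have a Phase B baseline and at least one post-randomization sodium, regardless of Phase B dosing. Keep the dose condition for the Safety Sample only.

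In SAP 5.1.7.2 item 2, state that for a Late Withdrawal subject with no Day 4 dose the endpoint is the sodium taken 24 hours after the nominal Day 4 dosing time. For a subject with no Phase B dose at all, this falls at 24 + 24 + 24 = 72 hours after the last dose, which matches the Early Withdrawal endpoint.

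Apply the definition to the summary statistics, and list undosed Late Withdrawal subjects with reasons.

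The cost is two SAP sentences and one listing. No new data are needed, because the protocol synopsis already schedules the draws: "All subjects will have serum sodium levels measured at 8, 12, and 24 hours post-first dose and thereafter every 12" (±4) hours to the end of Phase B. The by-arm difference may come out slightly smaller. No dosing or hold rule changes.

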5.1.2 Handling of Missing Data

For the primary endpoint analysis, missing data will be handled by analysis of mixed-model repeated measures (MMRM) methodology under the assumption of missing at random. The MMRM analysis will be performed based on the observed cases (OC) data. In order to assess sensitivity of results due to missing data, the last observation carried forward (LOCF) analysis will be performed as a sensitivity analysis. In contrast to the OC dataset, which will consist of the actual observations recorded at each visit, the LOCF dataset will include data recorded at a scheduled visit (ie, all OC data, or, if no observation is recorded at that visit, data carried forward from the previously scheduled visit). Baseline data will not be carried forward to impute missing values for the LOCF dataset.

5.1.3 Randomization

Eligible subjects will be randomized in a 1:1 ratio to either the Early Withdrawal group or the Late Withdrawal group. Randomization will be stratified by age [REDACTED]
[REDACTED], serum sodium response [REDACTED], and underlying hyponatremia etiology [REDACTED]
[REDACTED].

5.1.4 Baseline Characteristics and Baseline Comparability

In general, baseline measurements of efficacy and safety variables are defined as their last measurements prior to the first dose of IMP in the corresponding phases.

Demographic characteristics and medical history at Screening will be summarized by descriptive statistics, eg, proportion, mean, median, SD, minimum and maximum values. Use of concomitant medications prior to the start of IMP will be summarized by number and percentage of users by treatment group. These summary statistics will be reviewed to identify any potential lack of balance between the treatment groups.

Baseline characteristics will be summarized for Treatment Phase A and Treatment Phase B, respectively. Baseline characteristics by age categories [REDACTED]

[REDACTED] and by disease etiology [REDACTED]
[REDACTED] will also be provided.

5.1.5 Treatment Compliance

Treatment compliance will be calculated by dividing the total dose taken by the total dose the subjects are scheduled to take during the trial. For the Early Withdrawal subjects, the subjects are not scheduled to take the IMP in Treatment Phase B, the compliance will be 100% for these subjects unless they accidentally take the IMP.

5.1.6 Protocol Deviations

Major protocol deviations data will be summarized by type of deviations (eg, deviations in entry criteria, dosing, randomization, concomitant medication, procedural, etc) by center and treatment group. In addition, a subject listing will be provided describing the deviations for each subject.

5.1.7 Primary Outcome Analysis

5.1.7.1 Analysis of the Primary Outcome Endpoint

The primary endpoint in this trial is the change in serum sodium level for responders from Day 2 (or 2a) at the end of Treatment Phase A (where all subjects receive tolvaptan) to the end of Treatment Phase B for the Early compared to Late Withdrawal groups. The null hypothesis of this comparison is that there is no difference between the Late and the Early Withdrawal groups in change of serum sodium level from Day 2 (or 2a) at the end of Treatment Phase A to the end of Treatment Phase B. The analysis of the primary endpoint is based on the Treatment Phase B Efficacy Sample. Once a subject is randomized to Treatment Phase B, any additional therapies for the purpose of raising serum sodium, including fluid restriction, will be considered rescue therapy. Upon receipt of rescue therapy, a subject's endpoint data will be collected and then censored from the efficacy analysis thereafter unless specified. The primary analysis of this protocol is based on the data collected in this manner.

A sensitivity analysis will be provided in which serum sodium data collected for an Early Withdrawal subject under fluid restriction will not be censored for the analysis of the primary endpoint. This sensitivity analysis would become the primary analysis if at least 30% of the Early Withdrawal subjects do not have serum sodium data at 24 and 48 hours postrandomization due to application of fluid restriction in the withdrawal phase of the protocol.

The MMRM analysis with an unstructured variance covariance structure based on the OC dataset will be performed on the primary endpoint. The MM [REDACTED] clude

fixed effect of treatment, age subgroup [REDACTED], serum sodium response subgroup [REDACTED], underlying etiology [REDACTED], visit, treatment visit interaction, and covariate of baseline and baseline visit interaction. A statistical test of the least squares (LS) mean differences between treatment groups at the end of Treatment Phase B of the MMRM analysis will serve as the primary analysis.

As a sensitivity analysis, analysis of covariance (ANCOVA) with baseline value as covariate and treatment, age subgroup, serum sodium response subgroup, and underlying etiology of hyponatremia as factors will be applied to the LOCF dataset. Treatment comparison between the Late and Early Withdrawal groups will be conducted by comparing their LS.

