### **3.2.4.3 Fluid Restriction Considerations**

In subjects with chronic hyponatremia, fluid restriction coadministered with initiation of treatment with a vaptan has the potential to accentuate the rate of sodium correction and to cause overly rapid correction or over correction of hyponatremia. Therefore, during treatment, subjects must have access to water and maintain fluid intake levels per institutional guidelines. Fluid restriction at any time during the trial including during the first 48 hours after discontinuation of tolvaptan will be considered rescue therapy.

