## **7.4 Primary and Secondary Outcome Analysis**

### **7.4.1 Primary Outcome Analysis**

The primary endpoint in this trial is the change in serum sodium level for responders from Day 2 (or 2a) at the end of Treatment Phase A (where all subjects receive tolvaptan) to the end of Treatment Phase B for the Early compared to Late Withdrawal groups. The null hypothesis of this comparison is that there is no difference between the Late and the Early Withdrawal groups in change of serum sodium level from Day 2 (or 2a) at the end of Treatment Phase A to the end of Treatment Phase B. The analysis of the primary endpoint is based on the Treatment Phase B Efficacy Sample. Once a subject is randomized to Treatment Phase B, any additional therapies for the purpose of raising serum sodium, including fluid restriction, will be considered rescue therapy. Upon receipt of rescue therapy, a subject's endpoint data will be collected and then censored thereafter. The primary analysis of this protocol is based on the data collected in this manner.

A sensitivity analysis will be provided to include serum sodium data collected while an Early Withdrawal subject is under fluid restriction for the analysis of the primary endpoint. This sensitivity analysis would become the primary analysis if at least 30% of the Early Withdrawal subjects do not have serum sodium data at 24 and 48 hours post-randomization due to application of fluid restriction in the withdrawal phase of the protocol.

The MMRM analysis with an unstructured variance covariance structure based on the OC dataset will be performed on the primary endpoint. The MMRM model will include fixed effect of treatment, age subgroup [REDACTED], serum sodium response subgroup ([REDACTED]), underlying etiology ([REDACTED] [REDACTED]), visit, treatment visit interaction, and covariate of baseline and baseline visit interaction. Statistical test of the least squares (LS) mean differences between treatment groups at the end of Treatment Phase B of the MMRM analysis will serve as the primary analysis.

As a sensitivity analysis, analysis of covariance with baseline value as covariate and treatment, age subgroup, serum sodium response subgroup, and underlying etiology of hyponatremia as factors will be applied to the LOCF dataset. Treatment comparison between the Late and Early Withdrawal groups will be conducted by comparing LS means.

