4.1 Sample Size for Efficacy

A total of 70 randomized subjects will provide 90% power to detect a treatment difference of 4 mEq/L (mmol/L) in change in serum sodium from Day 2 (or 2a) at the end of Treatment Phase A to the end of Treatment Phase B using a 2-sided alpha of 0.05. A standard deviation (SD) of 5 in change of serum sodium was used for the sample size calculation. After the end of Treatment Phase A at Day 2 (or 2a), subjects will be randomized at a ratio of 1:1 to either continue treatment with tolvaptan for 2 additional days (Late Withdrawal) or to discontinue tolvaptan treatment (Early Withdrawal). Sample size re-estimation will be conducted when 90% of the randomized subjects finish (complete or discontinue) the trial.

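### The fluid-restriction analysis that can replace the primary keeps on-restriction sodium for Early Withdrawal only, so the two arms are compared under different rules for the same post-randomization event

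*SAP*

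**What the plan says.** SAP 5.1.7.1 sets a general rule for everyone randomized into Phase B: "any additional therapies for the purpose of raising serum sodium, including fluid restriction, will be considered rescue therapy". Endpoint data are collected on receipt of rescue and censored afterwards unless the SAP specifies otherwise. Protocol 7.4.1 gives the same rule without the closing proviso. Protocol 3.2.4.3 puts no arm limit on it either: "Fluid restriction at any time during the trial including during the first 48 hours after discontinuation of tolvaptan will be considered rescue therapy". The rescue definition in SAP 5.1.7.2, item 5, also covers any level of fluid restriction in any subject.

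The one exception specified is the sensitivity analysis in which "serum sodium data collected for an Early Withdrawal subject under fluid restriction will not be censored for the analysis of the primary endpoint". Protocol 7.4.1 has the same one-arm wording: the analysis is "to include serum sodium data collected while an Early Withdrawal subject is under fluid restriction". In both documents it takes over as primary if at least 30% of Early Withdrawal subjects have no sodium data at 24 and 48 hours because of fluid restriction.

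Three other places bear on the point. Protocol 3.2.4.2 labels rescued Late Withdrawal subjects treatment failures, stops their trial treatment and moves them to Phase C. Protocol 3.8.3 says rescued subjects continue to be monitored per protocol. SAP 5.1 says that, after very low enrollment and early termination, the efficacy analyses need not be run beyond summary statistics.

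**The concern.** The exception names Early Withdrawal only, so Late Withdrawal stays under the general censoring rule. The Early mean then reflects sodium as observed, restriction included. The Late mean is a mixed-model estimate under missing at random (SAP 5.1.2), as if restriction had not occurred. The difference between them answers neither question cleanly.

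This would matter less in a purely supportive analysis. Here a prespecified trigger can make it the confirmatory test, in an open-label trial where the decision to intervene rests with the investigator and local practice. Part of the resulting difference would come from the handling rule and not from tolvaptan.

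**Working it through.** **Inputs from the documents** (SAP 4.1). "A total of 70 randomized subjects will provide 90% power to detect a treatment difference of 4 mEq/L (mmol/L"), "using a 2-sided alpha of 0.05". "A standard deviation (SD) of 5 in change of serum sodium was used for the sample size calculation". Allocation: "subjects will be randomized at a ratio of 1:1", so 35 per arm.

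**Reproducing the plan's figure.** The normal formula n = 2(1.960 + 1.282)² × 5² / 4² gives 32.8, so 33 per arm and 66 in total. The t-test version gives 34 per arm (68 in total, power 0.902). At 35 per arm, power is 0.910 (t) or 0.917 (normal). The planned 70 is consistent with its inputs.

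**The trigger.** 0.30 × 35 = 10.5, so 11 Early Withdrawal subjects.

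**Assumptions, not in the documents.** Let pE and pL be the shares restricted in the Early and Late arms, and e the rise in endpoint sodium caused by restriction. I take pE = 30%, pL = 5-20% and e = 2-4 mEq/L. For now, censored data are missing at random and tolvaptan continues after restriction. Powers use the normal approximation at 35 per arm and SD 5.

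**Expected Late-minus-Early difference when the planned difference is 4:**
- Both arms censored (default primary): 4.
- Early-only rule: 4 − pE·e.
- Same rule in both arms: 4 − pE·e + pL·e.

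The term pE·e is what the sensitivity analysis is meant to show. The asymmetry itself contributes only pL·e: from 0.05 × 2 = 0.1 to 0.20 × 4 = 0.8 mEq/L.

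| e | Early-only, pE = 30% | Both arms kept, pL = 10% |
|---|---|---|
| 2 | 4 − 0.6 = 3.4, power 0.81 | 3.4 + 0.2 = 3.6, power 0.85 |
| 4 | 4 − 1.2 = 2.8, power 0.65 | 2.8 + 0.4 = 3.2, power 0.76 |

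**No true difference, equal share p restricted in both arms.** One rule for both arms gives 0; the Early-only rule gives −p·e. The standard error is 5 × √(2/35) = 1.195.
- p = 10%, e = 2: shift 0.2, two-sided rejection 5.3%. At 10% the switch could not fire.
- p = 30%, e = 4: shift 1.2, two-sided rejection 17.1%. Since 1.2/1.195 = 1.004, rejection in tolvaptan's favor is P(Z < −1.960 − 1.004), about 0.15%, against a nominal 2.5%. The remainder points the other way.

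**Why these figures are not bounds.**
- If restricted Late subjects are doing worse than the model predicts from unrestricted Late subjects, censoring them raises the Late mean and favors tolvaptan.
- Under Protocol 3.2.4.2 a rescued Late subject also stops tolvaptan. Later values then reflect restriction plus loss of drug, a net effect that could have either sign.

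**Whether the values would exist.** The Late endpoint is the 24-hour trough after the Day 4 dose (SAP 5.1.7.2, item 2). For a Late subject rescued after the Day 3 dose, that time is 48 hours after the last dose. Phase C schedules sodium at 72 hours and 7 days after the last dose (Protocol 3.1.1.3). Protocol 3.8.3 and SAP 5.1.7.1 suggest collection continues, while Protocol 3.2.4.2 suggests the subject has left the Phase B schedule.

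**The case against.** The strongest reply is that the rule was aimed where the problem was expected. Protocol 3.2.4.3 requires access to water and maintained fluid intake during treatment, because restriction alongside a vaptan may correct sodium too fast. Restriction should therefore be less common in the arm still on tolvaptan, and with no restricted Late subject the asymmetry changes nothing. This stands as a limit on size. It does not justify leaving the Late arm under a different rule, since a common rule costs nothing when the event is rare.

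A second reply is that SAP 5.1 makes the matter largely moot, because no mixed model need be run. That also stands and limits the consequence to the planned rule.

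A reader might infer three stronger claims that the documents do not support:
- *That the rule inflates false positive claims for tolvaptan.* Under missing at random it does the reverse: nearly all of the 17.1% is rejection against tolvaptan. Bias in its favor needs restricted Late subjects to do worse than the model predicts, which is possible but cannot be quantified here.
- *That the rule breaches the stated intent-to-treat principle.* Protocol 7.2 and SAP 5.1.1 use that principle to define the sample, and this rule removes no subject. The default primary, which censors both arms, departs further from keeping data regardless of rescue.
- *That the Late sodium data are already in hand.* The sections on rescue leave this unclear, as shown above.

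**Conclusion.** The point holds as a defect in the planned confirmatory rule. Late censoring is not written in the sensitivity paragraph itself. It follows from a general rule covering every randomized subject and a sole exception that names Early Withdrawal, and nothing elsewhere lifts it for Late Withdrawal.

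Size and direction are undetermined. The 0.1-0.8 mEq/L illustration rests on assumed shares and an assumed effect, on missing at random, and on tolvaptan continuing after restriction, which Protocol 3.2.4.2 contradicts. A reader should not take it as a range for the true bias, nor infer that a reported confirmatory result is distorted, because SAP 5.1 calls only for summary statistics. The change is worth making because it is cheap and removes an avoidable source of bias from an analysis that can become primary.

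**What to change.** In SAP 5.1.7.1 and Protocol 7.4.1, state that for this analysis serum sodium collected under fluid restriction will not be censored in either group. Keep censoring for other rescue therapies as now.

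Reconcile Protocol 3.2.4.2, Protocol 3.8.3 and the collection statements in Protocol 7.4.1 and SAP 5.1.7.1 on two matters: what the treatment-failure label means for the analysis of rescued Late Withdrawal subjects, and whether their Phase B sodium is still collected through the endpoint time. This point takes no position on how those subjects should be managed.

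The cost is wording in two documents, plus confirmation that the Phase B values are captured. There is one downside to accept openly: retained values from restricted Late subjects may include time off tolvaptan, so for fluid restriction the contrast becomes a treatment-policy one, comparing assigned strategies and not continued drug against withdrawal. The SAP should say so.
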